## 4.0 Study Endpoints\*

### 4.1 Primary endpoint

The primary endpoints of this pilot trial are:

1) Feasibility: We will determine the optimal strategy to achieve a high retention rate and adherence to the study protocol. We will also assess retention rates (proportion of included patients completing T2 follow up; we will target >70%), fidelity to the study protocol (Borrelli et al criteria; we will target >90%) and the Feasibility of Intervention Measure (FIM, 4 items, see Appendix 1. 3-month Follow Up Assessment (T2); we will target an average score of >3).

2) Acceptability: We will determine the acceptability of the AUDIO intervention and study protocol by assessing the proportion of patients and clinicians who agree to take part in the project and proportion of patients who listen to the recording. Our primary indicator of acceptability will be the recruitment of 108 participants (N=30 patients and 6 clinicians per site) over our planned data collection period of six months. We will determine the listening rates (we will target >70%): this will include the proportion of patients in the intervention arm that log in to the online system and listen to (and how often) the recording. We will also document the number of patients who share or report sharing the recording and caregivers who access the recording. Participants will complete the Acceptability of Intervention Measure (AIM, 4 items, see Appendix 1. 3-month Follow Up Assessment (T2); target an average score of >3).

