## 6.0 Procedures Involved

**Study Design:** We will conduct a multi-site, two-arm, parallel group, patient-randomized, blocked, controlled, pilot trial with 3-month follow up, to determine the impact of sharing audio recordings of clinic visits (AUDIO) on self-management in older adults with diabetes and hypertension, compared to the AVS alone (Usual Care). We will recruit 108 adults (30 patients and approximately 6 clinicians per site),  $\geq 65$  years with diabetes and hypertension over a recruitment period of 3 months. We are primarily interested in determining the feasibility of the trial and acceptability of the AUDIO intervention. We will also explore the impact on the patients' ability to self-manage their care as well as exploratory outcomes, at baseline (T0 = pre-visit) and at regular intervals from enrollment (T1 = 1 week, T2 = 3 month). We will also adhere to the CONSORT Statement extension to randomized pilot and feasibility trials during the trial, publish a study protocol and register the study on ClinicalTrials.gov. Our decision to use a patient level randomized trial design is justified for several reasons: 1) randomization reduces the impact of selection bias and confounding; 2) the risk of contamination is low as audio recordings will be reviewed outside of the clinic and the information will be unique to the each patient; 3) individual-level randomization is more efficient than cluster (e.g. clinic) randomization; 4) the use of blocking further improves the statistical precision of results by ensuring that the key characteristics are balanced across treatment groups, avoiding reliance on statistical models to adjust for any imbalances and 5) we will set up routine evaluations of key operational features of the study design e.g., recruitment rates, intervention use, fidelity - determining the need to make changes/refinements to study procedures throughout the trial.

**6.1 Randomization process:** Patients will be randomly allocated to AUDIO or UC alone using a block-randomization technique with the clinician acting as the blocking variable. Blocks of 2 patients per clinician will be generated to ensure an equal number of patients per clinician will be randomly assigned to the AUDIO and UC arm. The

PROTOCOL TITLE: *The impact of sharing audio recorded clinic visits on self-management in older adults: a multisite trial*

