where quantifies the extent to which the patient's HL modifies the effect of AUDIO on PAM-SF. A in (2) implies that the effect of AUDIO is lower in patients with high HL and higher in patients with low HL. We will also explore whether the impact of audio recording is greater for individuals at highest risk of poor self-management including those with moderate to severe depression and high disease burden. The variables described for the exploratory analyses will be analyzed using the model in (2) to form an analogous series of secondary and extended analyses for depression, anxiety, stigma and disease burden. Furthermore, we will examine whether 1) the presence of a caregiver or 2) sharing information (recording or AVS) with a caregiver moderates the impact of audio on PAM-SF. We will repeat these analyses to explore interaction effects by sex, race and ethnicity (**Sex as a Biological variable**), reporting interaction size and statistical significance.

**17.1.9 Appropriateness of Study Design:** The use of patient level randomization greatly

**PROTOCOL TITLE:** *The impact of sharing audio recorded clinic visits on self-management in older adults: a multisite trial*

simplifies the statistical analysis plan. Due to randomization, there is no need to include an elaborate array of predictors in the statistical model. Because patients are randomized the impact of clustering by clinician and site on standard errors will be minimal, however we will check to assure comparability of groups at baseline and control as needed. In fact, clinician and site act as blocks as we balance the proportion of patients assigned to AUDIO and UC within each of them to guard against the possibility that by chance any clinicians ended up with all patients being assigned to a given group and to maximally gain from the statistical efficiencies of a balanced design. That is, we essentially have a randomized block design. This allows analyses for site and clinician to be control variables whose inclusion sharpens the precision of our inferences, which are determined primarily off variation within clinician and site

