## 26.0 Multi-Site Research\*

This is a multi-site study that will involve 3 sites and a total of 30 patients and 6 clinicians recruited per site for a study total of N=108 participants (90 patients and 18 clinicians). All procedures (identification, recruitment, consent, data collection) described above will be followed at each site. REDCap will be used to gather, share and store data securely, across all sites.

Weekly meetings will be planned between the MPIs ([name], Dartmouth; [name], VUMC; and [name], UTMB).

**26.1 Organization structure.** Drs. [name], [name] and [name] will co-lead all aspects of the project: administrative, technical and scientific. We will complete and keep up-to-date the WORKSHEET: Communication and Responsibilities (HRP-830) and all PIs will be responsible for sharing the most current version of the protocol and consent documents with their study teams. [name] will serve as the Contact PI and will assume fiscal and administrative management and responsibility of the project. He will be responsible for communication with NIH and submission of annual reports. All PIs will be responsible for oversight of the project, including maintaining communication with

**PROTOCOL TITLE:** *The impact of sharing audio recorded clinic visits on self-management in older adults: a multisite trial*

each other, key personnel, and project staff through scheduled weekly meetings. Each PI will be the primary responsible party for all activities at their respective site. During weekly meetings, the PIs will meet with site coordinators to discuss study progress e.g., recruitment and retention rates, protocol adherence and data quality. Should concerns arise such as recruitment rates falling below target thresholds, mitigation plans will be generated and the trial steering committee will be informed and a meeting will be convened to determine if changes in protocol are required. Significant changes in protocol will be communicated with the IRB and approved. PI [name] will be responsible for creation of annual reports, publication of trial protocol on ClinicalTrials.Gov and coordination of manuscript and conference proceedings to emerge from the project, with support from both PIs [name] and [name]. Publication authorship will be based on the relative scientific contributions of project personnel. The Trial Steering Committee and MPIs will work together to identify lead, senior and contributing authors.

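### Blocking on clinician does not balance patient characteristics, and the two data-dependent covariate rules give up precision in the AUDIO effect on PAM-SF

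*Combined protocol and SAP*

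**What the plan says.** Section 6.0 (Study Design) gives as one reason for the design that blocking improves precision by "ensuring that the key characteristics are balanced across treatment groups, avoiding reliance on statistical models to adjust for any imbalances". Section 6.1 then allocates patients "using a block-randomization technique with the clinician acting as the blocking variable", and adds: "Blocks of 2 patients per clinician will be generated to ensure an equal number of patients per clinician". No patient characteristic is a stratification factor.

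Model (1) in section 17.1.3 always contains site indicators and a clinician random effect. For anything further, section 17.1.9 says that "there is no need to include an elaborate array of predictors in the statistical model", followed by "we will check to assure comparability of groups at baseline and control as needed". It names no covariates, no test and no threshold.

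The baseline (T0) value of the outcome has a rule of its own in section 17.1.5. T0 goes in as a covariate if baseline and follow-up values cluster strongly within patients, with an intra-class correlation above 0.5 as the example. The same section accepts that including T0 may improve precision.

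Sections 12.0 and 17.1.10 say that the pilot will estimate effect sizes precisely enough to inform sample-size calculations for a later trial, and that it is not powered for outcome differences.

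**The concern.** The balance claimed in section 6.0 is wider than the design delivers. Pairs within clinician do nothing to balance health literacy, disease burden, depression or baseline activation, several of which section 17.1 lists as marking patients at high risk of poor self-management.

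The plan then relies on two rules that look at the data before fixing the model. A comparability check adjusts when imbalance is conspicuous, but the gain from a prognostic covariate does not depend on conspicuous imbalance. Moderate imbalance that passes the check stays in the estimate. Dropping T0 when its correlation with the outcome is moderate likewise discards information already collected. What is at stake is the precision of the AUDIO effect on PAM-SF, and its independence from analyst choice.

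**Working it through.** **Inputs from the documents.** 3 × (30 + 6) = 108 participants, of whom 90 are patients: 45 per arm and 90/18 = 5 per clinician on average. At the 70% retention threshold of section 4.1, 0.70 × 90 = 63 patients reach T2, or 31.5 per arm (32 below). The documents state no power, effect size or SD, so there is no power figure to reproduce.

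**Assumptions.** The check is a two-sided 5% test at baseline; the effect is 0.5 SD; the covariate-outcome correlation is r. None of these is in the documents.

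**1. Chance imbalance left by blocking on clinician.** For a patient characteristic unrelated to clinician, the SD of the standardised arm difference is √(2/n).
- 45 per arm: √(2/45) = 0.211. P(|difference| > 0.2 SD) = 2[1 − Φ(0.2/0.211)] = 34%.
- 31.5 per arm: √(2/31.5) = 0.252, giving 43%.
- A characteristic with 50% prevalence, 45 per arm: 1.96 × √(2 × 0.25/45) = 0.207, so the 95% range of the arm difference is ±21 percentage points.

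**2. What a 5% check lets through.** Largest unflagged difference: t(0.975, 88) × √(2/45) = 0.42 SD. In simulation (18 clinicians × 5 patients, blocks of 2, clinician as fixed effects, clinician intra-class correlation of 0.02 assumed), about 29% of trials had a difference above 0.2 SD that stayed unadjusted.

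**3. Precision.** Fixed adjustment multiplies the variance by 1 − r²: 0.91, 0.84 and 0.75 at r = 0.3, 0.4 and 0.5. Ninety patients then act like 90/0.91 = 99, 90/0.84 = 107 and 90/0.75 = 120. Simulated SE in SD units, with 45 per arm and no effect:

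| r | No adjustment | Check, then adjust | Always adjust |
|---|---|---|---|
| 0.3 | 0.217 | 0.215 | 0.207 |
| 0.5 | 0.213 | 0.207 | 0.187 |

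The check recovers (0.217 − 0.215)/(0.217 − 0.207) = 20% of the available reduction in SE at r = 0.3, and (0.213 − 0.207)/(0.213 − 0.187) = 23% at r = 0.5.

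**4. Power at T2, 32 per arm, effect 0.5 SD.** Unadjusted SE = √(2/32) = 0.25, so effect/SE = 2.00 and power is about 50%. Adjusted at r = 0.3: SE = 0.25 × √0.91 = 0.238, ratio 2.10, power about 54%. At r = 0.4: SE = 0.25 × √0.84 = 0.229, ratio 2.18, power about 57%. Simulation agrees: about 48-51% under check-then-adjust against 52-58% with fixed adjustment, over r = 0.3-0.4.

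**5. Validity.** Simulated type I error of the check rule was 5.2% at r = 0.3 and 4.6% at r = 0.5, so it is not inflated. Over all randomisations the estimate is unbiased. In trials with an unflagged difference above 0.2 SD favouring AUDIO, the estimate was shifted by about 0.09 SD (r = 0.3) to 0.13 SD (r = 0.5); with fixed adjustment the shift was about zero.

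**6. The T0 rule.** With similar variances at T0 and follow-up, an intra-class correlation of 0.5 is roughly r = 0.5. Leaving T0 out just below that cut-off forgoes up to 0.5² = 25% of the variance.

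**The case against.** The strongest reply is that the plan already adjusts for more than section 17.1.9 suggests, and that little depends on this comparison. Much of that stands.

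- A reader might infer that every covariate waits on the comparability check. That is wrong: site and clinician are in model (1) unconditionally, and T0 follows the clustering rule, which does not look at balance.
- Health literacy enters model (2) in section 17.1.8 as a main effect and an interaction, whatever the balance. Section 17.1.9 is therefore not its only route into an analysis. But model (2) is a moderator analysis and does not adjust the main AUDIO estimate.
- Section 17.1.9 mentions no significance test. The 5% check is an assumption, and a looser check would recover more of the precision.
- A reader might put in a high correlation and see a large loss: at r = 0.7 and 45 per arm, simulated power is 65% against 89%. The documents give no basis for such a value for age, the Charlson index or SAHL-E. The natural candidate is T0 PAM-SF, and at that level the section 17.1.5 rule would include it.
- PAM-SF is exploratory (section 4.2), and section 17.1 calls the analysis principally descriptive, so lost power is a weak harm in itself. Lost precision still matters, because sections 12.0 and 17.1.10 justify the sample by the precision of the effect estimates.
- Section 6.0 does not say which characteristics it means, and 17.1.9 correctly describes clinician and site as the blocks. That makes the first part a correction of wording, but a needed one, because section 6.0 uses the claim to argue against adjustment.

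**Conclusion.** The point holds in a limited form. Blocking balances clinician and site, not patient characteristics generally. The check-then-control rule and the clustering rule for T0 both let the data choose the model and forgo precision that fixed adjustment would provide.

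The cost is modest: roughly 4 to 7 percentage points of power in the illustration with 32 per arm, a 0.5 SD effect, a 5% check and r = 0.3-0.4, and up to a quarter of the variance if T0 is dropped just below its cut-off. A reader might go on to infer a biased AUDIO effect or an inflated false-positive rate. Neither follows: the shift in step 5 is conditional on a chance imbalance, and the SE already allows for it. The feasibility and acceptability endpoints are untouched. The change is worth making because it is cheap and improves the estimate the next trial will use.

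**What to change.** - **Section 17.1.9:** replace the check-and-control rule with a short fixed covariate set in model (1), used whatever the observed balance: the T0 value of the outcome, age and the Charlson index. Section 13.1 extracts age and the Charlson conditions before recruitment.
- **Section 17.1.5:** drop the clustering threshold, so that T0 is always included.
- **SAHL-E:** add it only if it is recorded before allocation. The documents do not state when it is given.
- **Timing of T0:** section 6.0 allows pre-visit surveys to be completed after the visit. Record whether each T0 PAM-SF preceded allocation, and state in advance how later values are handled, for example as missing baseline data under the imputation in section 17.1.7.
- **Baseline tables:** keep them descriptive, with no role in choosing the model.
- **Section 6.0:** limit the balance claim to clinician and site, and remove the statement that adjustment is avoided.

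The cost is wording in three sections and one degree of freedom per covariate: three, or four with SAHL-E. Apart from the T0 timing flag, no new data are needed.

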## **17.2 Qualitative Data analysis plan (Aim 2 debrief interviews)**

Content analysis will be used to code and analyze qualitative data, informed by the CFIR constructs, and guided by a consensual approach. [name] will oversee key stages (e.g. development and application of code book, creation of memos and themes) to ensure rigor of the process and increase the validity of findings. All interviews will be transcribed using a HIPAA compliant medical transcription company and de-identified transcripts will be imported to NVIVO which has a CFIR constructs coding template. RCs at each site will independently review and code the same transcripts, one from each stakeholder group, using the CFIR constructs. Codes will be developed in a manner similar to the “template approach” using *a priori* domains from CFIR and additional categories that emerge from inductive review of transcripts and field notes. Coded data will be aggregated and reviewed within and across codes. Coders will meet by web conference to compare codes, discuss disagreements, and settle on a final codebook with definitions and examples. To ensure consistent application of the codebook, coders will independently review every fourth transcript from another site and compare codes. Based on aggregated codes, summary memos will be created using the CFIR constructs and organized into a matrix of barriers/facilitators (major/minor) by site and CFIR construct. We will adhere to the Consolidated criteria for Reporting Qualitative research (COREQ) checklist.

PROTOCOL TITLE: *The impact of sharing audio recorded clinic visits on self-management in older adults: a multisite trial*

**17.3 Data security:** Our research team is experienced in training, instrument construction, editing, and data management. We will use the same procedures for data acquisition and management used in prior studies, including: (1) a common core of initial and refresher training for the research team; (2) continuous team feedback to the site; and (3) final data editing and management at our institute, The Dartmouth Institute, Lebanon, NH.

**17.3.1 Training:** All members of the research team and clinic staff will be trained in the study protocol and will have completed appropriate CITI training. The MPIs and research staff will meet weekly by WEBEX, from the time of study award, to plan protocol implementation at each site. Additionally, in month 6, a two-day 'kick off' training event will be hosted at Dartmouth College, and all study team members will join in person and/or virtually. During this training event, we will review and train research coordinators and assistants in all aspects of the study protocol including identification of patients, screening administration, recruitment and consent, survey administration and follow-up calls and plans for unexpected events. All RAs and site leads/coordinators will receive training in the identification, recruitment, consent, intervention and assessment administration. Training will involve role-play and feedback, as well as piloting of the entire recruitment process supervised by site PIs at each clinic.

**17.3.2 Protocol Adherence:** A fidelity checklist will be used (see Appendix. 16 Fidelity Checklist) to ensure the standard delivery and receipt of the audio recording. RAs will complete the checklist during initial recruitment and interim follow-up visits, documenting deviations from protocol and reasons. Site PIs will administer the fidelity checklist on 10% of the sample (approximately 3 patients per site), checking for 1) protocol adherence and 2) high agreement between their fidelity assessment and the RAs. Deviations from the protocol will be reported to the PIs and a mitigation plan developed during the weekly PI meeting. Participants from all sites will be given the option to contact the Dartmouth-Hitchcock Health (D-HH) Human Research Protection Program (HRPP), if they are dissatisfied or concerned about any aspect of the project; this information will be shared in the consent form.

We will use a direct-entry of data collected to a HIPAA compliant web-based system for data collection, REDCap, at all study sites during the trial for both in-clinic and telephone outcome assessments. This system provides entry validation range tests for all fields, as well as default (missing) values. All study data will be identified only with study ID numbers. The database will be protected by daily backup. PI [name] will monitor weekly data quality checks of the REDCap database, where all study data will be held, carried out by the project coordinator (e.g. extent of missing data). Prior to analyses, data will be exported from the entry database into statistical analysis packages (e.g.,

PROTOCOL TITLE: *The impact of sharing audio recorded clinic visits on self-management in older adults: a multisite trial*

Stata, SPSS, R) with complete labeling intact (variable names, variable labels, value labels, and missing value declarations). All clinic recordings will be labeled by participant number only. In all Aims participant identification numbers will be a sequential series (e.g., 1001, 1002, 1003) and the crosswalk to the participants' names will be kept separate from data and in a password-protected, encrypted file on a password-protected, HIPAA-compliant, secure server to which only the research team will have access, behind a restrictive firewall. To maximize data capture, patients can choose to complete baseline assessment using a paper form. These forms will be labeled with a patient unique identifier and entered immediately into REDCap by the RA.

**17.4 Health Information Sharing and Security:** An AVS will be offered to patients per the usual practice at their clinic, either printed or via the patient portal. Audio-recordings will be made available in via a HIPAA-compliant website developed for a related project, requiring a participant- specific username and password, which will be shared with patients on a paper card and by email. The web platform for recorded visits also provides a solution for patients to share their clinic visit information with their family and caregivers using a secure web application. This data-sharing mechanism will enable patients to share specific or all existing/incoming clinic visit recordings with another individual. The selected individual would receive an invite to the web platform through an email provided by the patient, and is required to register in our web application to have access to the visit recordings. Data- access privileges can be revoked by the patients, or study team, at any time. All patient data will be encrypted in a database residing within a Virtual Private Cloud which itself is within Dartmouth's domain on Amazon Web Services. Data will be managed in accordance with privacy and security policies that are consistent with the HealthCare Information Security and Privacy Practitioner Standards. All communication with the platform's servers will also be encrypted. See Appendix 5 for further information regarding the study's server infrastructure and security-related practices.

**17.5 Data quality:** Data quality is the responsibility of the research staff at the site under the supervision of the site PI. The RC, under the supervision of the site PI, is responsible for ensuring the accuracy, completeness, legibility, and timeliness of the data reported. Data, both clinical and patient reported assessments, will be directly entered into case report forms developed using REDCap. Separate Case Report Forms will be created for Screening data (including demographics); assessment (baseline(T0), T1, T2,); and intervention use. The data system includes password protection and internal quality checks, such as automatic range checks, to identify data that appear inconsistent, incomplete, or inaccurate. Clinical data will be entered directly from the source documents (EMR). Quality control (QC) procedures will be implemented beginning with the data entry system (REDCap) and data quality control checks that will be run on the database will be generated. Any missing data or data anomalies will be

PROTOCOL TITLE: *The impact of sharing audio recorded clinic visits on self-management in older adults: a multisite trial*

communicated to the site(s) by the project coordinator for clarification/resolution, and reported to PIs and Trial Steering Committee.

Any Quality Control issues arising from this monitoring will be reported by Contact PI [name] to the other PIs and Trial Steering Committee during weekly team meetings. Action (further training, protocol change) will be considered, and if a protocol change is deemed necessary, it will be reported to the study Funder and IRB of Record. The investigational site will also provide direct access to all trial related sites, source data/documents, and reports for monitoring and auditing by the sponsor, and inspection by IRB and DSMB, if required.

